**Investigation of the Effects of Bisphosphonate on the
Gingival Crevicular Fluid Levels of Sclerostin and the
DKK-1 in Individuals with Postmenopausal
Osteoporosis with Periodontal Changes**

Document Date: December, 2018

Uploaded: September, 2020

Study Protocol

Individuals with chronic periodontitis and osteoporosis between 51 and 66 years (mean age: 57.15 ± 4.93) (group A, n=12), 52 to 66 years (mean age: 57.41 ± 4.94) with systemic healthy chronic periodontitis (group B, n=10), between the ages of 50-63 (mean age: 55.64 ± 3.79) periodontally healthy osteoporotic individuals (group C, n=11) and 52-64 years (mean age: 56.55 ± 4.06) periodontal and systemically healthy individuals (group D, n=10) were included in study. 43 postmenopausal women in total were included in the study. This study involved postmenopausal women admitted to the Ondokuz Mayıs University Faculty of Medicine, Department of Endocrinology and Metabolism between 2016 and 2018. The study protocol was approved by Ethical Board of Ondokuz Mayıs University School of Medicine (OMU KAEK 2016/100) and was carried out in accordance with the ethical standards established in the 1964 Declaration of Helsinki, as revised in 2008. Written informed consent was obtained from each subject before enrollment in the study.

Bisphosphonates were started in the patients who were diagnosed with osteoporosis. Individuals smokes, who had received antibiotic treatment in the last 3 months and/or periodontal treatment in the last 6 months were excluded from the study. Following medical

record retrieving, patients were leaded to Ondokuz Mayıs University Faculty of Dentistry Periodontology Department for periodontal examination, receipt of clinical records and gingival crevicular fluid (GCF) samples. Following the receipt of medical records; standard periodontal recordings including plaque index (PI) (1), gingival index (GI) (2), bleeding on probing index (BOP), pocket depth measurement (PD), clinical attachment loss measurement (CAL), dental radiographs were received from each patient. Clinical measurements were taken from the region under each tooth (mesio-vestibule, mid-vestibule, disto-vestibule, mesio-lingual, mid-lingual, disto- lingual) using Williams probe. In the first clinical and radiographic evaluation, groups with postmenopausal osteoporosis and healthy groups were divided into 2 subgroups as chronic periodontitis and healthy control groups. The diagnosis of chronic periodontitis was made clinically and radiographically according to the criteria determined by the “1999 Periodontology Workshop” (3). Periodontitis patients consisted of patients with 4 or more probes with bleeding index (BOP) positive, 5 mm or more deeper pocket depth (PD) and ≥ 6 mm attachment loss (CAL) and radiographically determined alveolar bone loss. Individuals with <3 mm PD and no radiographically determined alveolar bone loss were preferred to form groups with healthy periodontium. In the groups with chronic periodontitis gingival

crevicular fluid (GCF) was collected with the help of periopaper (Periopaper®; Oraflow, New York, NY, USA) from the regions with the deepest pocket depth with periodontal defect, and in healthy groups it was collected by taking the right mandibular molar region as reference. Each time, the volume value of the collected GCF was determined by the Periotron 8000 device. GCF collected paper strips were placed in eppendorf tubes and stored at -80 ° C until biochemical analysis was performed (NUAIRE Ultra-Low Freezer Model no: Nu-6420E). Following the initial sample collection and recording of patient data (medical, periodontal and radiographic), patients were placed under phase 1 periodontal treatment (scaling and root planing), and oral hygiene habits of the patients were corrected and followed up for 1 year. In this period, periodontal treatments, controls and sample collections of the patients in Group A and Group B who completed phase 1 treatment were repeated at the end of 6th month and at the end of the 12th month after the end of the treatment, their clinical changes were recorded. The clinical data and GCF SOST and DKK-1 levels of osteoporosis groups (Group A and C) and non-osteoporotic chronic periodontitis group (Group B) with bisphosphonate were reevaluated in the determined times.

Biochemical Analysis

SOST and DKK-1 levels in gingival crevicular fluid were determined by ELISA (Enzyme-linked immunosorbent assay) kits (SunRed Human DKK1 ELISA Kit, Cat.No:201-12-063, and SunRedHuman SOST ELISA Kit, Cat No: 201-12 -5418) The SOST and DKK1 assay ratios according to the manufacturer's instructions are 0.2-60 ng / mL 0.5-78 ng / mL, respectively. Sensitivity is 0.412 ng / mL for DKK-1 and 0.17 ng / mL for SOST. Color intensity is measured at 450 nm and the results were calculated using standard curves for each kit. GCF SOST and DKK-1 concentrations were obtained by dividing total amount of SOST and DKK1 values by GCF volume (microliter). Concentration values will be presented in ng / mL.

Statistical Analysis

Statistical analysis was performed using SPSS (version 21, SPSS Inc. Chicago, IL, USA) program. The Shapiro-Wilk test was used to show if the data were consistent with the normal distribution. Comparisons of biochemical data between groups were performed with non-parametric Kruskal-Wallis test and $p <0.05$ was considered as statistically significant. In determining the

difference group, p value was divided by the number of comparison and $p < 0.016$ was accepted as significance level (Mann-Whitney U test with Bonferroni correction). Friedman test was used to determine the time difference in groups and $p < 0.05$ was considered as statistically significant.

3. Armitage GC. Development of a classification system for periodontal diseases and conditions. *Ann Periodontol* 4,1:1-6, 1999.

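### Bisphosphonate use follows the osteoporosis diagnosis and the before-after tests have no control, so no stated test isolates the drug effect named in the title

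*Combined protocol and SAP*

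**What the plan says.** The title begins "Investigation of the Effects of Bisphosphonate on the" and goes on to name GCF sclerostin and DKK-1. It is the only statement of aim; there is no objectives section.

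The Study Protocol section ties the drug to the diagnosis: "Bisphosphonates were started in the patients who were diagnosed with osteoporosis". It describes no randomisation, no osteoporotic group left untreated, and no clear statement that non-osteoporotic women were treated. Besides Group A (12 women with osteoporosis and periodontitis), the groups are:

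- women "with systemic healthy chronic periodontitis (group B, n=10")
- "periodontally healthy osteoporotic individuals (group C, n=11")
- "periodontal and systemically healthy individuals (group D, n=10")

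After the first sample, "patients were placed under phase 1 periodontal treatment (scaling and root planing), and oral hygiene habits of the patients were corrected", with follow-up for one year. Groups A and B are named as completing this periodontal treatment, with repeat sampling at 6 and 12 months. A later sentence lists A, C and B as re-evaluated; D is not listed. That sentence mentions bisphosphonate directly after Group B, so it is unclear which groups the word describes.

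The Statistical Analysis section compares groups by Kruskal-Wallis (p<0.05), then pairwise Mann-Whitney (p<0.016). For change over time, "Friedman test was used to determine the time difference in groups". It states no comparison of change between groups.

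**The concern.** A drug effect needs a contrast in which drug status differs and the other influences on SOST and DKK-1 do not. The plan offers two kinds of contrast, and they fail for different reasons.

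Between groups, drug and osteoporosis go together. A difference between A and B, or between C and D, could come from the disease, the drug or both.

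Within a group, disease status is constant, so confusion of drug with disease is not the issue. The issue is the missing control. In Group A the drug, scaling and root planing, hygiene correction and a year of time all fall in the same interval. In Group C the drug and time coincide, together with any hygiene correction given there. C has no untreated osteoporotic comparator, and D, its periodontally healthy counterpart, is not among the groups followed.

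At stake is the conclusion itself: a reader of the title would expect a statement about the drug that these tests cannot supply.

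**Working it through.** **1. Group sizes.** 12 + 10 + 11 + 10 = 43, which agrees with "43 postmenopausal women in total were included in the study".

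**2. Drug and disease by group**, applying the diagnosis rule:

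| Group | n | Osteoporosis | Periodontitis | Drug |
|---|---|---|---|---|
| A | 12 | 1 | 1 | 1 |
| B | 10 | 0 | 1 | 0 |
| C | 11 | 1 | 0 | 1 |
| D | 10 | 0 | 0 | 0 |

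Both: 12 + 11 = 23. Neither: 10 + 10 = 20. The osteoporosis and drug columns are identical. A 43-row design matrix with intercept, osteoporosis, periodontitis and drug has four columns and rank 3, so no between-group analysis can estimate drug and disease effects separately.

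**3. If Group B was treated.** Setting drug = 1 for B gives rank 4. Both A and B are then on drug, so A versus B contains no drug contrast. An additive model across all four groups could in principle estimate a drug term, but the plan fits no such model.

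**4. Between-group test with no drug effect.** This is an illustration. Assume normal data and an osteoporosis-only difference between A (n=12) and B (n=10); the sizes of the difference are assumptions, not figures from the documents. Simulated Mann-Whitney at the plan's p<0.016:

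| Assumed disease difference | Significant |
|---|---|
| 0.25 SD | about 2% |
| 0.5 SD | about 8% |
| 1.0 SD | about 33% |

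Using exact rather than approximate p-values moves these by no more than about three percentage points. Requiring a significant Kruskal-Wallis test first can only lower them.

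**5. Friedman with no drug effect.** Assume normal data, within-woman correlation 0.5, and one shift present at both 6 and 12 months that is due only to time or periodontal care (5000 runs):

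| Assumed shift | A | B | C |
|---|---|---|---|
| 0.5 SD | 32% | 22% | 24% |
| 1.0 SD | 83% | 71% | 76% |

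The test does what it should, which is to detect change. It cannot say what caused the change.

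**6. Significant in one group but not in another.** Give A and B the same 1.0 SD shift. Treating the groups as independent, the chance that A is significant and B is not is 0.834 × (1 − 0.713) = 0.239, about 24%. That pattern is not evidence that the groups changed differently.

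**The case against.** The strongest reply is that this is an observational study, that each stated test is a legitimate procedure for the comparison it makes, and that no sentence attributes a test result to the drug. All of that stands. The causal wording is confined to the title, and whether a result would be reported as a drug effect is a prediction. The point is therefore about what may be claimed.

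Four stronger readings are tempting, and the documents do not support them.

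- *No woman without osteoporosis took the drug.* This is the natural reading of the diagnosis rule, but it is an inference, because the re-evaluation sentence is ambiguous about Group B.
- *Untreated osteoporosis explains a significant Friedman result.* A stable disease difference cannot produce change within a group. That reading needs a disease-related drift over the year, and the documents give no evidence for or against one.
- *The percentages in step 4 are inflated false-positive rates.* They are the chance of detecting a real group difference; the error lies in attributing it to the drug. Setting them against a nominal 5%, or computing them for a t-test at 0.05, would describe an analysis that the plan does not contain.
- *A change contrast between A and B would repair the claim.* It removes stable disease differences and the periodontal treatment the two groups share. It still carries any difference in course between osteoporotic and other women, and it depends on the first sample preceding the drug, which the text does not say.

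**Conclusion.** The point holds in this form: no stated test isolates an effect of bisphosphonate. Between groups, drug and disease coincide in all 43 women (23 with both, 20 with neither) if the diagnosis rule was followed and Groups B and D were untreated. Within groups, the comparison is uncontrolled. If Group B was in fact treated, the first statement changes but the conclusion about the stated tests does not.

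The structural result needs no assumed effect size. The percentages in the working are illustrations under assumed shifts and normal data. The documents do not show how large a disease difference or time drift is, or that a drug effect is absent.

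This should be fixed rather than treated as invalidating the study: the stated procedures can stand, and the remedy is mainly the claim.

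**What to change.** 1. Restate the title, aim and conclusion as GCF SOST and DKK-1 levels, and their change, in osteoporotic women starting bisphosphonate compared with non-osteoporotic women, with no causal drug claim.
2. Do not rest a drug conclusion on Friedman p-values in A or C, or on one group being significant and another not. Report the A-versus-B difference in 12-month change directly, with a 95% CI. A rank-based method suits the plan (for example Mann-Whitney on change with a Hodges-Lehmann interval); a baseline-adjusted model is an alternative if its residuals allow. Label the result osteoporosis plus bisphosphonate.
3. Beside it, state that a drug reading requires that untreated osteoporotic women would have changed as Group B did. State whether the first GCF sample preceded drug start; the label in item 2 is right only if it did.
4. Report Group C's change descriptively, as uncontrolled.
5. Reconcile the re-evaluation sentence that mentions bisphosphonate after Group B with the diagnosis rule, so that each group's drug status is explicit.

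This needs no new patients, samples or assays. It costs rewording, one extra analysis in 22 women (12 + 10), whose interval may be wide, and a less favourable headline claim.

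### Should the plan have combined the two osteoporosis comparisons (A against B, C against D) into one baseline test using all 43 women?

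*Combined protocol and SAP*

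**What the plan says.** The Study Protocol section gives four groups: A (osteoporosis and chronic periodontitis, 12), B (chronic periodontitis, systemically healthy, 10), C (osteoporosis, periodontally healthy, 11) and D (healthy on both counts, 10). It states that "43 postmenopausal women in total were included in the study" and that "groups with postmenopausal osteoporosis and healthy groups were divided into 2 subgroups as chronic periodontitis and healthy control groups".

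Crevicular fluid was taken "from the regions with the deepest pocket depth with periodontal defect" in the periodontitis groups, whereas "in healthy groups it was collected by taking the right mandibular molar region as reference". Phase 1 periodontal treatment is placed later: "Following the initial sample collection and recording of patient data". On the drug, the section says "Bisphosphonates were started in the patients who were diagnosed with osteoporosis", without timing this against the first sample. Groups A, B and C are listed as re-evaluated; D is not.

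The Statistical Analysis section plans a Kruskal-Wallis test between groups at 0.05, Mann-Whitney pairs at a Bonferroni-corrected 0.016, and a Friedman test within groups over time. It describes no stratified, pooled or two-factor comparison, and it does not name the pairs or the visit behind 0.016.

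**The concern.** Each woman is classified on two factors, osteoporosis and periodontitis, but the analysis treats the result as four unordered groups. The Kruskal-Wallis test can use all 43 women, yet it does not isolate osteoporosis. The pairs that do, A-B and C-D, each set aside about half the sample.

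Combining them also looks sound in design. Sampling site follows periodontal status, so A-B and C-D each compare women sampled under the same site rule, and a stratified combination keeps that match. With groups of 10 to 12, halving the variance matters: a real difference in sclerostin or DKK-1 between women with and without osteoporosis could be missed in both pairs and found in the combination.

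**Working it through.** **The plan's own figures.** 12 + 10 + 11 + 10 = 43, as stated. A-B uses 12 + 10 = 22 women and C-D uses 11 + 10 = 21. For the threshold, 0.05/3 = 0.0167, which gives 0.016 if truncated; 0.05/6 = 0.0083. So 0.016 fits three comparisons, not all six baseline pairs. The documents give no effect size, SD or power calculation to reproduce.

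**Precision.** In SD units the variance of a difference in means is 1/n₁ + 1/n₂.

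- A-B: 1/12 + 1/10 = 0.183; half-width 2.086 × √0.183 = 0.89 SD (20 df).
- C-D: 1/11 + 1/10 = 0.191; half-width 2.093 × √0.191 = 0.91 SD (19 df).
- Combined by inverse variance: 1/(1/0.183 + 1/0.191) = 0.0935; half-width 2.023 × √0.0935 = 0.62 SD (43 − 4 = 39 df).
- Difference between the two effects (interaction): 0.183 + 0.191 = 0.374; half-width 2.023 × √0.374 = 1.24 SD.

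The combined variance is about half that of either pair (ratios 0.51 and 0.49). This depends only on the group sizes. As an estimate of one osteoporosis effect, however, it presupposes that the two strata share one.

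**Power.** Simulation used 40,000 runs per setting, normal data, exact Mann-Whitney tests, and a van Elteren test as the stratified comparison. All effect sizes are assumptions, including a 1 SD periodontitis effect. The plan column takes A-B and C-D as two of three pairs at 0.016, tested after a significant Kruskal-Wallis test. The last column counts the stratified test as a fourth comparison, with A-B, C-D and the stratified test each at 0.05/4 = 0.0125 and no Kruskal-Wallis requirement. Power means that at least one of these tests is significant.

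| Assumed osteoporosis effect (periodontitis stratum, healthy stratum) | Plan | With stratified test |
|---|---|---|
| 1.0 and 1.0 SD | 59% | 73% |
| 0.8 and 0.8 SD | 40% | 51% |
| 1.0 and 0.5 SD | 41% | 50% |
| 1.0 and 0 SD | 37% | 37% |
| +1.0 and −0.5 SD | 42% | 38% |

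The gain is real when the effects are similar, nil when only one stratum has an effect, and negative when they oppose. In the last case the combined estimate is expected near 0.51 × 1.0 − 0.49 × 0.5 ≈ 0.27 SD, which describes neither stratum. The interaction test has only 36% power for a 1 SD difference, so the data could not reliably show which row applies.

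**False positives.** Under the assumed 1 SD periodontitis effect, the rate for an osteoporosis finding goes from 2.9% to 2.8%, which looks free of cost. That depends on the periodontitis effect, which often makes the Kruskal-Wallis test significant and so opens the way to the plan's pairs. Without it, the rate rises from 1.9% to 2.8%. Keeping the pairs at 0.016 and adding the stratified test at 0.0125 gives 3.4% instead of 2.9%, again with the 1 SD periodontitis effect. All of these stay below 5%, but the addition is not free.

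**Relevance.** The title asks about bisphosphonate. Group D is not listed as re-evaluated, so the two-by-two layout exists only at baseline and cannot bear on change under the drug. Nor do the documents say whether the first sample came before the first dose, so the baseline contrast may mix osteoporosis with early drug exposure. A narrower interval does not remove that.

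**The case for a change.** The strongest case for the addition is that it costs almost nothing. It needs no new data and, before tie correction, follows from the two Mann-Whitney statistics: z = [(U_AB − 60)/23 + (U_CD − 55)/22]/0.923. It replaces no existing result and gives the tightest site-matched baseline estimate these women allow. If only one of A-B and C-D was among the planned pairs, the plan's power at 1.0 SD is just 36% or 37%, so there is more to gain.

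The counts, the variance ratio and the power figures for equal effects all stand. They show that a useful supplementary estimate exists; they do not show that leaving it out is an error. The document is dated December 2018 and reports its methods in the past tense, so the test would be post hoc and would carry little confirmatory weight. It could not safely replace the pairs either. Alone at 0.0125 it has 69% power at 1.0 SD in both strata, but 13% if the effect is in one stratum only and 2% at +1.0 and −0.5 SD. An estimate on the log scale would also need a rule for values below the assay limits ("Sensitivity is 0.412 ng / mL for DKK-1 and 0.17 ng / mL for SOST").

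That the pairs and the visit behind 0.016 are not named is a true gap in reporting. It is a separate point, and a stratified test would not close it.

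**Conclusion.** The concern does not hold. Kruskal-Wallis followed by corrected Mann-Whitney tests is a conventional choice for four small groups, and following it gives no wrong result. The test said to be missing targets a baseline average osteoporosis effect that no passage sets as an aim.

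What stands is a trade-off. A stratified comparison would narrow the half-width from 0.89 or 0.91 SD to 0.62 SD. It would raise power by 14 points (73 − 59) at an assumed 1.0 SD in both strata, leave it unchanged with an effect in one stratum only, and lower it by about 4 points (42 − 38) with opposite effects. The documents neither support nor exclude similar effects. These figures rest on the stated group sizes, normal data and, for power, assumed effects with both A-B and C-D among the planned pairs. An analyst may reasonably add the comparison as a labelled post hoc estimate; the plan is not at fault without it.

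### The A-versus-B biomarker comparison uses no covariate, although the groups are not randomised and baseline pocket depth and baseline biomarker levels were recorded

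*Combined protocol and SAP*

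**What the plan says.** **Group formation.** The Study Protocol section describes groups defined by diagnosis: "groups with postmenopausal osteoporosis and healthy groups were divided into 2 subgroups as chronic periodontitis and healthy control groups". Group A is given as "mean age: 57.15 ± 4.93) (group A, n=12" and group B as "52 to 66 years (mean age: 57.41 ± 4.94", "with systemic healthy chronic periodontitis (group B, n=10". Bisphosphonate was started in the women diagnosed with osteoporosis. No randomisation or matching is described.

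**Severity and sampling.** Entry to either periodontitis group needs positive bleeding, radiographic bone loss and "5 mm or more deeper pocket depth (PD) and ≥ 6 mm attachment loss (CAL". These are lower limits, and no upper limit is set. In A and B the crevicular fluid comes from the deepest diseased pocket.

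**What was recorded.** PD, CAL, plaque, gingival and bleeding indices were recorded in each patient. "Clinical measurements were taken from the region under each tooth", at six named sites. Fluid was sampled at the start and again at months 6 and 12 in A and B.

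**Analysis.** The Statistical Analysis section says "Comparisons of biochemical data between groups were performed with non-parametric Kruskal-Wallis test" (at 0.05), then Mann-Whitney U at p < 0.016 to locate differences, and Friedman tests for change within groups. It names no covariate, stratum or model. It does not list the pairs compared or the visits at which the between-group tests are made.

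**The concern.** Two groups that only have to exceed the same floor can still differ in how far above it they lie. Sampling the deepest pocket carries that variation into the assay. If SOST or DKK-1 in the fluid is related to pocket severity, a severity difference between A and B becomes part of the A-B biomarker difference. It could produce a difference where osteoporosis status has no effect, or mask one where it does.

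The contrast matters for the follow-up. Groups A, B and C are re-evaluated, but C is sampled at a fixed molar region rather than the deepest pocket. A versus B is therefore the only follow-up contrast that has both a common sampling rule and a group without osteoporosis.

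Precision is also lost. With 12 and 10 women, ignoring a related baseline value gives up power that measurements already taken could recover.

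**Working it through.** **1. The plan's own threshold.** 0.05/3 = 0.0167, which gives 0.016 only if truncated. All six pairs of four groups would give 0.05/6 = 0.0083. Three re-evaluated groups make three pairs, so 0.016 is consistent with A-B being tested, although the plan does not say so. The documents give no sample-size, power or effect-size figure to reproduce.

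**2. Age (stated figures).**
- Pooled SD = sqrt[(11 × 4.93² + 9 × 4.94²)/20] = 4.93 years.
- Difference A − B = 57.15 − 57.41 = −0.26 years. Standardised: −0.26/4.93 = −0.05.
- 95% CI of the difference: −4.7 to 4.1 years.
- With an assumed age-biomarker correlation of 0.2-0.6, the bias is about 0.01-0.03 SD in size. That is negligible.

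**3. Pocket depth (no group values given).** The inputs are assumptions: a PD-biomarker correlation of 0.4-0.6 and a systematic A-B gap of 0.5-0.8 SD. Spurious difference = correlation × gap:
- low end 0.4 × 0.5 = 0.20 SD;
- high end 0.6 × 0.8 = 0.48 SD.

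**4. False positives.** Simulation of 12 v 10 women, normal data, no true A-B effect, cut-off 0.016. The first grid (20,000 runs per cell) uses the large-sample Mann-Whitney test and a linear model adjusted for baseline PD and age:

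| Correlation | PD gap (SD) | Mann-Whitney | Adjusted |
|---|---|---|---|
| 0.3 | 0 / 0.5 / 1.0 | 1.1% / 1.5% / 2.8% | 1.6% / 1.7% / 1.6% |
| 0.5 | 0 / 0.5 / 1.0 | 1.1% / 2.4% / 7.0% | 1.6% / 1.7% / 1.7% |
| 0.7 | 0 / 0.5 / 1.0 | 1.1% / 3.7% / 14.3% | 1.7% / 1.4% / 1.7% |

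The same regression on ranks rejects 1.6-2.3%. Over the assumed range in step 3, with the exact Mann-Whitney test, the unadjusted rate is 2.5-7.6% (1.4-1.5% with no gap). With two covariates it is 1.0-1.7%.

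**5. Chance imbalance.** If A and B come from the same severity distribution, the SE of the standardised PD difference is sqrt(1/12 + 1/10) = 0.43. A gap above 0.5 SD then has a 24% chance, and one above 0.8 SD a 6% chance. Averaged over such chance gaps, the unadjusted test rejects about 1.2%, which is below nominal. Among samples whose observed gap is 0.5-0.8 SD, it rejects 1.5-4.3%.

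**6. Power for a true 1 SD difference at 0.016.**
- No PD gap, correlation 0.4-0.6: 36-37% unadjusted, 42-56% with two covariates.
- Group A's pockets 0.5 SD shallower: 17-22% unadjusted, 36-56% adjusted for PD.
- At zero correlation the first grid gives 33% unadjusted and 36% adjusted. A small part of the gain therefore comes from using a linear model on normal data, not from the covariate.

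The documents give no correlation between baseline and follow-up concentration, so no gain from that covariate is quantified here.

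**The case against.** The strongest reply is that nothing in the documents shows a severity gap. A and B met the same bleeding, PD, CAL and bone-loss criteria and were sampled by the same rule. No PD or CAL is given by group, and the correlation is assumed. This stands. The 2.5-7.6% is conditional on a systematic gap and is not an estimate for this study.

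Four stronger readings are tempting, and the documents do not support them.
- *Age is a neglected confounder.* The stated means differ by 0.26 years, so age would use up a covariate for almost nothing.
- *Chance imbalance in small groups inflates the error rate.* It does not (step 5). A particular imbalanced sample can mislead, but the overall rate stays at about 1.2%.
- *The plan reads an A-B difference as a bone or drug effect.* No sentence does so. The title frames the aim as the effect of bisphosphonate, and the rest is a risk of interpretation.
- *The sampled site's depth is on file for every sample.* Six-site charting makes the deepest PD probably retrievable, but no text links a paper strip to a charted site.

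Two further objections limit the remedy. Baseline PD may partly result from osteoporosis, and that applies to month 6 and 12 contrasts as well as baseline, so a PD-adjusted result should not displace the unadjusted one. And because bisphosphonate follows the osteoporosis diagnosis, no adjustment of A versus B can tell disease from drug.

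What remains is that shared floors do not equalise severity above them, the planned tests use none of the baseline data, and the precision argument does not require an imbalance.

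**Conclusion.** The concern holds in a limited form. The between-group biomarker tests carry no covariate, in a comparison of 12 and 10 women who were not randomised or matched. Baseline PD was charted and baseline SOST and DKK-1 were measured. Any difference in pocket severity that is related to the biomarker therefore enters the A-B contrast.

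The size of the distortion is unknown. It is 0.20-0.48 SD, with about 2.5-7.6% false positives at 0.016, only if the PD correlation is 0.4-0.6 and a systematic gap of 0.5-0.8 SD exists. If there is no gap, the unadjusted test keeps its error rate and the loss is one of power: 36-37% against 42-56% for a 1 SD effect under the same assumed correlations. These figures also assume normal data on the analysis scale.

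**What to change.** 1. Report baseline PD and CAL by group, so that readers can see whether A and B differ in severity.
2. For A versus B at months 6 and 12, add a rank ANCOVA, or a linear model on log concentration. Adjust for the woman's own baseline concentration of the same biomarker and for baseline PD. Use the deepest charted pocket, or the sampled site if its link to the fluid sample is confirmed. Use baseline PD only, because later PD is measured after periodontal treatment. Leave age out.
3. Show this beside the unadjusted Mann-Whitney result, and show the adjusted model with and without PD, because PD may lie partly on the path from osteoporosis.
4. State that the A-B contrast, adjusted or not, cannot separate osteoporosis from bisphosphonate.
5. Label the analysis as an addition to the stated plan, since the document is already written in the past tense.

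The cost is some wording, one further analysis on measurements the protocol says were taken, and a check of whether samples can be linked to sites. Statistically it uses two degrees of freedom: residual df fall from 22 − 2 = 20 to 18. With 22 women there is no room for a longer covariate list.

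### Does the single pairwise cut-off of 0.016 break down because Group C's follow-up sampling and the baseline pairs are left unclear?

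*Combined protocol and SAP*

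**What the plan says.** The Study Protocol section enrols four groups: A (12), B (10), C (11) and D (10), 43 women in all.

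On follow-up it has two adjacent sentences. The first says that "sample collections of the patients in Group A and Group B who completed phase 1 treatment were repeated at the end of 6th month", and again at 12 months. The second says that clinical data and the "GCF SOST and DKK-1 levels of osteoporosis groups (Group A and C) and non-osteoporotic chronic periodontitis group (Group B" were re-evaluated at the set times. The first names A and B; the second adds C.

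The Statistical Analysis section then sets out three tests:
- Between groups: "Comparisons of biochemical data between groups were performed with non-parametric Kruskal-Wallis test", at p < 0.05.
- To find which group differs: "Mann-Whitney U test with Bonferroni correction", where the "p value was divided by the number of comparison and $p < 0.016$ was accepted as significance level".
- Within groups: "Friedman test was used to determine the time difference in groups", at p < 0.05.

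Neither the pairs nor the visits for the between-group tests are named, and the divisor behind 0.016 is not stated.

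**The concern.** One cut-off appears to serve comparison families of different sizes. At baseline, four groups give six pairs, and a literal Bonferroni correction over all of them would need about 0.0083, roughly half of 0.016. That raises the possibility of too many false positives.

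At follow-up the worry runs the other way. If only A and B gave crevicular fluid samples at 6 and 12 months, there is a single pair, and testing it at 0.016 would be about three times stricter than necessary (0.05/0.016 = 3.1).

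Group C is the osteoporotic group without periodontitis. Whether it has later samples also decides whether it has a Friedman test, which bears on the study's question about marker levels under bisphosphonate.

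**Working it through.** **Reproducing the cut-off.** 0.05/3 = 0.01667, which truncates to 0.016 (rounding would give 0.017). The neighbouring divisors do not fit: 0.05/2 = 0.025 and 0.05/4 = 0.0125. So three comparisons are implied, and truncation makes the level slightly stricter than required.

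**Pairs available.** Two groups: 1. Three groups: 3. Four groups: 4 × 3/2 = 6.

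**Follow-up with A, B and C.** Three pairs, so 0.05/3 applies, and the bound is 3 × 0.016 = 0.048. Simulated family-wise error with all three groups equal and no Kruskal-Wallis condition: 3.3-4.0%.

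**Follow-up with A and B only.** The plan's first step is Kruskal-Wallis at 0.05. With two groups this is the same test as the asymptotic Mann-Whitney test without continuity correction. Once it is significant, there is no differing group left to find. Dividing by the number of comparisons also gives 0.05/1 = 0.05. The plan's own rule therefore tests A against B at 0.05, with simulated type I error of 5.1% and power of 58% for a 1 SD difference.

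**Which reading is natural.** The first follow-up sentence does not say that only A and B were sampled. It describes the patients who completed phase 1 treatment, together with their repeat treatments and check-ups. The second sentence lists SOST and DKK-1 levels for C explicitly, which requires samples. A divisor of 3 matches the three pairs among A, B and C and cannot arise from one pair. The text favours sampling of C.

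**Baseline, pairwise tests after Kruskal-Wallis p < 0.05.**
- All four groups equal: no pairwise false positive can be declared unless Kruskal-Wallis rejects first, which holds the error near or below 5%.
- One group differs: three pairs remain truly null, so the bound is 3 × 0.016 = 4.8%. With two equal pairs of groups, only two pairs are null: 2 × 0.016 = 3.2%.

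**Baseline simulation** (sizes 12/10/11/10, cut-off 0.016):

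| Procedure | Situation | Family-wise error |
|---|---|---|
| Three contrasts against D | all equal | 3.2-3.9% |
| Six pairs after Kruskal-Wallis | all equal | 3.8-4.1% |
| Six pairs after Kruskal-Wallis | one group shifted 0.5, 1 or 3 SD | 2.7-4.1% |
| Six pairs, with or without Kruskal-Wallis | two groups shifted 3 SD | 2.3-3.1% |
| Six pairs, no Kruskal-Wallis condition | all equal | 5.9-7.2% (bound 6 × 0.016 = 9.6%) |
| Six pairs, no Kruskal-Wallis condition | one group shifted | 3.1-4.2% |

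Each configuration used 100,000 simulated trials with normal data, equal variances and no dropout (Monte Carlo standard error at most about 0.16 percentage points). The ranges cover exact, asymptotic and continuity-corrected Mann-Whitney p-values, because the plan does not say which is used. The distribution and the shifts are assumptions; the documents give neither.

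**Change over time.** The Friedman test at 0.05 is run within each group. The 0.016 level does not enter it.

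**The case for a change.** The best case for a change is that the reader should not have to infer any of this. The two follow-up sentences do list different groups, the divisor is unstated, and the baseline pairs are unnamed. If only A and B were sampled and an analyst applied 0.016 mechanically, power for a 1 SD difference would be 33-36% instead of 55-58%, and for 1.5 SD 72-75% instead of 88-90%. If all six baseline pairs were tested without the Kruskal-Wallis condition, calling the procedure Bonferroni would be wrong.

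The mismatch in wording stands. The power loss does not, because it requires the plan to break its own rule by dividing by three when there is one comparison. The ungated six-pair procedure sits poorly with the text, which introduces the Mann-Whitney tests as the step that locates a difference.

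One limit also stands: the 0.016 level controls error for one biomarker at one visit. It does not adjust across SOST and DKK-1 or across visits. As an illustration, two independent markers at 4% each give 1 − 0.96² = 7.8%. That is a separate matter from the divisor.

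**Conclusion.** No change follows. On the natural reading, in which A, B and C have follow-up samples and pairwise tests come after a significant Kruskal-Wallis test, 0.016 keeps family-wise error below 5% per biomarker and visit: at most 4.0% in simulation at follow-up and 4.1% at baseline. On the A-and-B reading the plan's rule gives 0.05. Moving to 0.05/6 at baseline would protect against nothing on the natural reading, and would cut power for A against B at 1 SD from 33-36% to 24-27%.

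What remains is missing detail about which groups were sampled at each visit and which pairs were compared. The study's own tables of numbers by group and visit would show it. The conclusion rests on the pairwise tests following Kruskal-Wallis, or on no more than three baseline contrasts being tested, and on the simulation assumptions given with the figures.
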